Page 50 of 71 Treat to target in gout Protocol Final Version 1.1 date 29 May 2019

Definition of CKD

Incident CKD will be defined as eGFR<60ml/min on 2 occasions at least 90 days apart. The results of eGFR at year 1 and year 2 research assessments will form one of the two qualifying results. If the eGFR at these research assessments is <60ml/min, the GP surgery records will be searched to identify a serum creatinine measurement in the preceding six months, and, if no such result is found or the previous eGFR is >60 ml/min, the GP will be advised to repeat the serum creatinine after 90 days as part of usual care of people with suspected incident CKD.

Progression of CKD will be defined as reduction in GFR of at least 25% and progression to next GFR category (KDIGO Definition). The results of serum creatinine, eGFR and urine albumin creatinine ratio at year 1 and 2 research assessments will be used to define the progression of CKD.

The proportion of people meeting the KDIGO classification of progression of CKD based on their eGFR and urine albumin creatinine ratio will be compared between the two groups at years 1 and 2 [51].

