8.7 Assessment of efficacy

Table 12: Assessment of efficacy

Endpoints	Efficacy parameter	Timing	Timing
		RCT	extension
Primary			
Number of gout flares	Rate ratio	2 year	4 year
Secondary			
Pain severity during flare	Mean difference	2 year	4 year
Duration of flare	Mean difference	2 year	4 year
Generic HR-QoL (EQ-5D-5L) during flare	Mean difference	During flare	NA
Gout specific HR-QoL (GIS) during flare	Mean difference	During flare	
EQ-5D-5L HR-QoL between flares	Mean difference	1, 2 year	NA
Serum urate	Mean difference	2 year	NA
Serum creatinine and estimated GFR	Mean difference	2 year	NA
Urine albumin creatinine ratio	Mean difference	2 year	NA
Medication possession ratio	Mean difference	2 year	
Treatment acceptability questionnaire	Mean difference	2 year	
Healthcare utilization		2 year	4 year
Primary care consultations for gout	Mean difference	2 year	4 year
Hospitalizations due to gout flares	Mean difference	2 year	4 year
Current ULT		2 year	4 year
Number of ULT prescriptions	Mean difference		
No of prescriptions for treating flares	Mean difference	2 year	4 year
Cost-effectiveness		2 year	NA
Comorbidities			
Death	Hazard ratio	2 year	4 year
Chronic kidney disease progression	Hazard ratio	2 year	4 year
Ischaemic heart disease	Hazard ratio	2 year	4 year
Myocardial infarction	Hazard ratio	2 year	4 year
Stroke	Hazard ratio	2 year	4 year

median difference or rate ratio will replace mean difference, if appropriate

Page 54 of 71

Treat to target in gout Protocol Final Version 1.1 date 29 May 2019

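### The section 8.3 rule for progression of CKD requires neither CKD at entry nor a confirming result, so it bypasses the two-result rule for incident CKD, and it lacks the albumin-creatinine criterion the text says is used

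*Protocol*

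**What the plan says.** Section 8.3 (Definition of CKD) gives two rules side by side.

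- Incident CKD "will be defined as eGFR<60ml/min on 2 occasions at least 90 days apart". A year 1 or year 2 research result supplies one of the two. If it is below 60, the GP record for the preceding six months is searched. If that holds no result, or one above 60, "the GP will be advised to repeat the serum creatinine after 90 days as part of usual care of people with suspected incident CKD".
- The second rule, for worsening disease, states that progression "will be defined as reduction in GFR of at least 25% and progression to next GFR category", and labels this as the KDIGO definition. A further sentence, on how progression is judged, opens with these words: "The results of serum creatinine, eGFR and urine albumin creatinine ratio at year 1 and 2 research assessments will be used to define the". No repeat test is mentioned.

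The planned comparison is then stated: "The proportion of people meeting the KDIGO classification of progression of CKD based on their eGFR and urine albumin creatinine ratio will be compared". It is made by trial arm, at years 1 and 2.

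The outcome appears in combined form (incidence or progression of CKD) in sections 6.1.2 and 6.3.2, and section 8.5 analyses it by a time-to-event model. Table 12 in section 8.7 gives "Chronic kidney disease progression" its own row, with a hazard ratio at 2 and 4 years.

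**The concern.** The two rules feed one outcome but set different standards of proof. A participant who enters without recognised CKD and has one low result is not an incident case until a second result confirms it. The same single result can make that participant a progression case at once. In the combined outcome, the stricter rule can then be passed over whenever the fall reaches 25% and crosses a category boundary.

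Three things are at stake. The outcome mixes worsening of existing CKD, new decline in people not shown to have CKD, and one-off falls from test variation or transient illness. The Table 12 row, which isolates progression, carries a label that its events may not deserve. And an analyst cannot apply the albumin-creatinine ratio, because the text invokes it without a criterion. Section 8.3 tests each outcome at p ≤ .05 without multiplicity adjustment, on the ground that each matters in its own right, so the definition of this one matters too.

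**Working it through.** The plan gives no figure for this outcome, so there is none to reproduce. The check applies the printed rules.

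**Inputs from the protocol**
- Progression: fall of at least 25% plus a move to the next GFR category (8.3).
- Incident CKD: eGFR below 60 on two occasions at least 90 days apart (8.3).
- Entry: only eGFR below 30 ml/min is excluded (6.7.2), so people without CKD can enter.
- Reference value: creatinine at the screening visit, with no repeat stated (6.7.1, Table 11). Urine is collected at baseline, year 1 and year 2 (Table 11).
- Printed eGFR cuts: 60 and 30 only. I treat 60 as a category boundary; the full category list is not printed.

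**Step 1: the two rules compared**

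| | Incident CKD | Progression of CKD |
|---|---|---|
| Entry status required | not stated, but implied by incident | not stated |
| Results needed after entry | two, at least 90 days apart | one |
| Record search or repeat | yes | none stated |
| Albumin-creatinine term | none, none claimed | none, but said twice to be used |

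**Step 2: one worked case.** Screening eGFR 80, year 1 eGFR 58.
- Fall = (80 − 58)/80 = 22/80 = 27.5%, which is at least 25%.
- 80 to 58 crosses 60, so the category changes. Progression is met on one result.
- Incident CKD: one result below 60. Not met until a second is found.
- Suppose a repeat 90 days later reads 75. The fall is then (80 − 75)/80 = 6.25%, and incident CKD is refuted. The progression flag stays, because no sentence lets the repeat cancel it. The participant is still counted in the combined outcome.

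**Step 3: the albumin-creatinine ratio.** The defining sentence has two conditions, both on GFR. The two sentences after it say that the ratio is used. All three cannot be followed together.

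**Step 4: how many could be affected (illustration only).** Every input here is assumed, including category cuts at 90, 60, 45, 30 and 15.
- First set: entry eGFR mean 60, 70 or 80 with SD 17–18, entry at least 30; test-to-test CV 8% or 12%; mean decline 0 or 3% a year with SD 5%. Between 3.4% and 16.7% of participants meet the rule at one or both annual visits, and 0.3% to 3.3% at both. Of those flagged, 61% to 92% had entry eGFR of 60 or more. Of those flagged at year 2, only 9% to 49% had eGFR of 60 or more both at entry and at year 2.
- Second set: mean 70–80, SD 18; CV 6%–10%; decline 0 or 1 ml/min/year. Between 0.1% and 8.5% are flagged, 45% to 94% of them with entry eGFR of 60 or more, and 0.1% to 1.3% if both visits must show the fall.

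The ranges are wide because the documents do not fix the inputs. They show direction: a second result removes most flags. Requiring both annual visits is stricter than a 90-day repeat and also removes true declines that appear only by year 2.

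**The case against.** The strongest reply is that progression of CKD, with a KDIGO label and citation, presupposes CKD, and that denominators and confirmation rules for a secondary outcome are usually left to the SAP, which section 8.1 says takes precedence. The first part is a fair reading, but the text does not state it, and it would supply neither a confirming test nor an albumin-creatinine criterion. The second part would hold if the protocol were silent. It is not: it prints a rule, gives confirmation to one half of the outcome only, and misdescribes the role of the urine ratio.

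A second reply is that the overlap does little harm, since the listed outcome is a composite. That would be so if both routes set the same standard; here one route avoids the other's confirmation. Table 12 also isolates progression.

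A third reply is that single-test variation occurs in both arms and mainly dilutes a difference. No directional bias is shown, and that stands. It is not guaranteed to be neutral, though: the side-effect tables list raised creatinine for febuxostat and naproxen, whose use may differ by arm.

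Two stronger readings are tempting and not supported:
- A reader might infer that most counted cases would be people who never had CKD. The documents give no eGFR distribution or CKD prevalence, and the simulated shares rest on assumptions and fall below half in places. An eGFR of 60 or more does not by itself exclude CKD when the urine ratio is also part of the assessment.
- A reader might take a fall from 95 to 70 as the telling case. It counts only if a category boundary lies between those values, and the protocol prints none there.

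**Conclusion.** The point holds as a fault in a printed rule. Section 8.3 lets one result count as progression of CKD in a participant not shown to have CKD, which bypasses the confirmation required for incident CKD in the same section. It also claims a use of the albumin-creatinine ratio that the definition does not contain. Both follow from the text; the 80-to-58 case additionally takes the printed value of 60 as a category boundary.

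The size cannot be stated from the documents, and the simulated figures are illustrations. The effect is confined to a secondary outcome and its Table 12 row. Serum creatinine, eGFR and the urine ratio are also compared directly as mean differences, so renal conclusions do not rest on this label alone. The primary outcome is unaffected. The definition should be corrected before the outcome is analysed.

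**What to change.** In section 8.3:

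1. Limit progression to participants with CKD at entry, defined from the screening eGFR and the baseline albumin-creatinine ratio, both already collected. Count everyone else only under the incident-CKD rule. A cut on eGFR alone would leave out people whose CKD is marked by albuminuria.
2. Require the fall to be confirmed by a second result at least 90 days apart, from the other annual visit or the GP record. Report unconfirmed falls separately.
3. Add the albumin-creatinine criterion, or delete the statements that the ratio is used.
4. Use the same definition for the Table 12 hazard ratio.

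The cost is mainly wording plus a wider GP-record search. It is not nil. The existing search starts only when the research eGFR is below 60, and the repeat only when the record holds no recent result or one above 60. A participant with known CKD and a recorded value below 60 would often trigger no repeat. There will be fewer progression events, so the Table 12 hazard ratio will be less precise, and some falls first seen at year 2 may stay unconfirmed.

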8.4 Health economic analysis

Cost-effectiveness (cost per flare avoided) and cost-utility (cost per quality-adjusted life year (QALY) gained) will be determined within the trial using healthcare resource use data (questionnaires and medical records), primary outcome data and EQ-5D-5L. The economic evaluation will assess the cost-effectiveness and cost-utility of treat-to-target with ULT compared with usual GP care in patients with recurrent gout. This will take the form of an incremental cost-utility analysis to estimate cost per QALY and an incremental cost-effectiveness and outcomes from the trial. The base-case analysis will be from an NHS and Personal Social Services perspective, with an additional analysis from a societal perspective taking into account productivity losses.

Data collection: In order to calculate QALYs, the EQ-5D-5L questionnaire will be administered to patients at baseline, 12 and 24 months. In order to account for quality of life during gout flares, participants will also complete the EQ-5D-5L once during each gout flare. The crosswalk value set will be applied to patient responses to obtain utility scores, in line with current NICE recommendations. The more recent English value set will be used in a sensitivity analysis. Information on gout-related resource use will collected via patient paper diary filled in prospectively over the 24-month study period. The cost of the intervention will be determined within the trial, taking into account nurse training, and costs of delivering the interventions. Unit costs from standard UK sources will be sought for all health care resource use items. Data on broader costs will also be collected, related to time off work to calculate productivity losses. Information on occupation, further details of typical work activities and the nature of their employment (full time or part time) will be requested. The average wage for each respondent will be identified using UK Standard Occupational Classification coding and annual earnings data for each job type.

Analysis: The number of gout flares per patient will be obtained from the trial. QALYs will be calculated using responses to the EQ-5D-5L, using the "area under the curve" approach. For patients with gout flares, this will also include EQ-5D-5L data collected for each flare, taking

Page 51 of 71 Treat to target in gout Protocol Final Version 1.1 date 29 May 2019

into account the duration of the flare, so that flare-related disutility is captured. Unit costs will be applied to all health care resource use items, and mean resource use (for each category of health care usage) and mean total costs will be calculated for all trial participants. Analysis of productivity losses will use the human capital approach, and the self-reported days of absence will be multiplied by the respondent-specific wage rate. The human capital approach assumes that the value of lost work is equal to the amount of resources an individual would have been paid to do that work, and values productivity losses as a result of morbidity (or mortality) by measuring time lost from work and multiplying this with the gross wage of the person. As cost data are likely to have a skewed distribution, the nature of the distribution of costs will be explored, and if the data are not normally distributed, a non-parametric comparison of means (using bootstrapping) will be undertaken. Multiple imputation will be used to impute all missing values for the EQ-5D-5L and total cost estimates for non-responders. A cost-consequence analysis will initially be reported, describing all the important results relating to costs and consequences (across the full range of clinical outcomes).

Incremental cost effectiveness analysis and cost-utility analysis will then be undertaken to estimate the incremental cost per gout flare avoided and incremental cost per QALY gained respectively. There will be adjustment for baseline covariates, as specified by the main statistical analysis. The robustness of the results will be explored using sensitivity analysis. This will explore uncertainties in the trial-based data, the methods employed to analyse the data, and the generalizability of the results to other settings. Cost-effectiveness acceptability curves will also be produced to reflect the probability that the intervention will be cost effective at different cost per QALY willingness to pay thresholds.

8.5 Long term follow-up

The data analysis in this phase will be conducted on the same lines as described in the RCT. Death, and incidence or progression of CKD, myocardial infarction, ischaemic heart disease, stroke will be analysed using a time-to-event survival model. ULT prescription will be included as a time-varying covariate in this analysis. A multivariable linear model will be used to compare healthcare utilization between the groups.

Interim analyses will inform efficacy and trial management. These results will be available to the main analysis team, and the outcome of these analyses may affect the conduct of the study. Unless other interim analyses are requested by the DMC, only one interim analysis is planned, at the end of the internal pilot.

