A recent Randomised Controlled Trial (RCT) from Nottingham (n=517) with communitybased recruitment and intervention delivery compared Academic centre based research nurse-led of care to usual (GP-led) care of people with gout over a two year period (11). The nurses were trained about gout and delivered a package of care reflecting recommended best practice (12,13), specifically: individualised holistic assessment with enquiry and discussion of illness perceptions; full information on the nature, causes, possible consequences and treatment options for gout (appendix 3); a treat-to-target ULT strategy; and full patient engagement in management decisions. Compared to usual care, nurse-led care resulted in very high ULT uptake (96% v 56% at year 2); achievement of target serum urate <360µmol/L in more patients (95% v 30% at year 2); lower flare frequency during year 2 (mean 1.5 v 2.4); reduced presence of tophi (3% v 11% at year 2); and improved quality of life (SF-36 physical component) at year 2. The intervention was cost-effective in improving patient-centred outcomes and modelled to be cost-saving at year 5. Flare frequency during year 1 was comparable in both arms (mean 3.6 vs. 3.5) possibly because only 3 participants in the nurse-led arm elected to have flare prophylaxis, even though this option was considered and discussed. Whether such care is generalizable and could be equally well delivered by non-research practice-based nurses, or other health professionals, is unknown. On post hoc analysis, the number of flares over the total two year treatment period were not statistically different between the two arms (MD unpublished data). Thus, it remains unknown if an allopurinol based treat-to-target ULT regime that included flare prophylaxis, reduces the number of gout flares from treatment initiation.

This lack of clarity has resulted in sub-optimal gout management and culminated in discordant recommendations from primary care and rheumatology gout treatment guidelines, exemplified by the recent American College of Physicians' recommendation to treat gout patients to avoid symptoms rather than treat to a target serum urate level, due to lack of high-quality RCT evidence [12–16]. Previous research has demonstrated that gout

Page 14 of 71 Treat to target in gout Protocol Final Version 1.1 date 29 May 2019

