4.4 LONG TERM EXTENSION

Primary objectives:

To evaluate the long-term effect of continued allopurinol-based treat-to-target ULT versus usual GP care on number of gout flares in years 3-4.

Secondary objectives

To evaluate the long-term effect of continued allopurinol-based treat-to-target ULT versus usual GP care on healthcare utilisation for gout in years 3-4, incidence of comorbidities, and mortality.

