7. TRIAL STUDY TREATMENT AND REGIMEN

7.1 Treatment in intervention arm:

Allopurinol-based treat-to-target ULT is the healthcare technology being assessed. It will be delivered by practice nurses trained in delivering and managing a protocol driven allopurinol-based treat-to-target regimen.

The steps of the treat-to-target ULT protocol are consistent with national and international recommendations and recent studies [12–14, 34–35]. These are:

 Allopurinol commenced at a dose of 100 mg/day at the baseline visit in the experimental arm. Participants already on sub-therapeutic dose of allopurinol will have its dose increased by 100 mg/day. Individualized education about gout and principles of management including treat-to-target-ULT discussed. Lifestyle riskfactors of gout discussed. Advice for improving them provided as adjuncts to treatto-target-ULT. Arthritis Research UK (recently renamed Versus Arthritis) leaflet on

> Page 37 of 71 Treat to target in gout Protocol Final Version 1.1 date 29 May 2019

gout provided.

- Participants of Han Chinese, Thai or Korean ethnicities will be commenced on Febuxostat 80 mg/day as first line ULT, as they are at a high risk of developing DRESS syndrome from Allopurinol treatment.
- A booklet containing study contact details, and a table for recording current ULT dose, serum urate level, date of next serum urate blood test, and date of next repeat ULT or flare prophylaxis prescription will be provided to participants in the intervention arm.
- Serum urate measured after 4 weeks, as serum urate is a negative acute phase reactant [13] and the urate level commonly reduces during a flare. If a participant is experiencing gout flare at this time, the visit will be postponed till 2 weeks after the flare has resolved completely. This is a treatment visit and will be conducted by general practice nurses, phlebotomists or other suitably trained staff.
- Allopurinol dose increased by 100mg/day if the serum urate is ≥360 µmol/L at week 4.
- Process repeated approximately 4-weekly until serum urate is <360 µmol/L, or maximum licensed or tolerated dose of allopurinol reached.
- Allopurinol discontinued if unable to achieve serum urate <360 µmol/L due to side effects or intolerance of high doses, or failure to do so despite maximum licensed dose, and febuxostat 80 mg/day started as per the NICE Technology Appraisal 164.
- The dose of febuxostat increased 4 weeks later to 120 mg/day if the serum urate ≥360 µmol/L.

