8.3 Full RCT

Analytical plan: Analysis will be on an intention-to-treat (ITT) basis, according to the prespecified SAP. The primary outcome, gout flare count over 24 month's post-randomization, will be analysed between groups through negative binomial regression, adjusting for flare count in the year prior to trial entry and stratification factor. If appropriate, a conditional, rather than a marginal, negative binomial model will be used to take account of flare count prior to trial entry (truncating these to be non-zero, in accordance with the corresponding inclusion criteria). The fit of a negative binomial model to the data will be assessed, and if poor, an alternative model (e.g. zero-inflated negative binomial or Poisson) will be used. As a secondary analysis on the primary outcome, flares occurring during months 1–12 and between months 13–24 will be analyzed between groups.

Longitudinal analyses based on generalized linear mixed-effects models will be performed for other continuous or binary outcomes, at both 1- and 2-year follow-up: mean pain intensity and mean duration of gout flares; mean serum urate; treatment satisfaction scores; adherence (those taking >80% of the doses or scoring ≥6 on the MMAS-8 will be considered as adherent) These analyses will similarly adjust for baseline values (where appropriate) and the stratification factor.

All analyses will take use all follow-up data where appropriate, using a generalized mixedeffects regression model, with a random intercept to account for the correlation between observations clustered within participants. Maximum likelihood estimation will be used to fit all the models, as this method of estimation yields parameter estimates that are not affected by the exclusion of missing outcome data if a missing-at-random assumption is plausible. Multiple imputation will be used for explanatory variables if missing at random is a plausible assumption.

Assumptions of all analyses will be checked and significance will be set at $p \le .05$, with 95% CIs calculated for between-group estimates. No adjustment will be made to alpha for multiplicity because the analysis of each outcome is of clinical interest in its own right. The primary analysis will be on the basis of ITT, but appropriate sensitivity analyses will be performed, as specified in the SAP.

Side-effects from intervention will be tabulated and compared between the two groups.

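### The long-term survival model for death, CKD and cardiovascular events adjusts for ULT prescription after randomisation, so its arm hazard ratio is not the intention-to-treat effect that the extension sets out to estimate

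*Protocol*

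**What the plan says.** Section 8.5 of the protocol states that death, incidence or progression of CKD, myocardial infarction, ischaemic heart disease and stroke "will be analysed using a time-to-event survival model", and then that "ULT prescription will be included as a time-varying covariate in this analysis". No second model without the covariate is described, and this one is not labelled supportive or mediational. The coding of the covariate (any or none, drug, dose) is not given.

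The same section opens with "The data analysis in this phase will be conducted on the same lines as described in the RCT". For the RCT, section 8.3 says "Analysis will be on an intention-to-treat (ITT) basis" and, of its models for other continuous or binary outcomes, "These analyses will similarly adjust for baseline values (where appropriate) and the stratification factor".

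The secondary objective in 4.4 begins "To evaluate the long-term effect of continued allopurinol-based treat-to-target ULT versus usual GP care on healthcare utilisation for gout in years 3-4" and goes on to name incident comorbidities and mortality. Section 8.7 (Table 12) gives the effect measure for these endpoints as a hazard ratio at 2 and 4 years.

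On the treatment side, 7.1 says "Allopurinol-based treat-to-target ULT is the healthcare technology being assessed". Control participants may also receive ULT from their GP (Synopsis, 5.5, 7.2). ULT prescriptions are listed in 6.3.2 as a secondary outcome of the extension.

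**The concern.** The extension asks what randomisation to the treat-to-target strategy does to mortality, renal disease and cardiovascular events. ULT prescription during follow-up lies on the path from allocation to those events. Conditioning on it compares the arms at equal prescription status, which is a different question. The part of any benefit or harm that works through being prescribed ULT is taken out of the arm coefficient.

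The covariate is also not assigned at random. Section 6.7.3 allows the treat-to-target regimen to be stopped for a contraindication and gives terminal illness as an example. In the control arm, 7.2 leaves ULT to the GP's usual practice and the participant's symptoms. Illness can therefore influence both prescription and the events being modelled. Once the model conditions on prescription, the arms are no longer balanced on such illness, and the arm coefficient is not clearly a direct effect either.

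At stake is the reading of the extension's most serious outcomes. The error can conceal harm as readily as benefit.

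**Working it through.** **Plan's own figure.** The protocol gives no event rate, hazard ratio, event target or power for these endpoints, so there is nothing to reproduce. What follows is illustrative.

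**Inputs from the document** (section 3, source trial, year 2, intervention v usual care)
- ULT uptake: "nurse-led care resulted in very high ULT uptake (96% v 56% at year 2").
- Target serum urate reached: 95% v 30%.

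**Assumptions**
- The mediator multiplies the hazard by h = 0.7 or h = 0.5.
- The covariate is coded any or none.
- Target urate is reached only on ULT.
- The source trial's year-2 figures hold throughout follow-up.

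**Arm hazard ratio without the covariate.** If proportions a and b of the two arms have the mediator, the ratio of average hazards is

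HR = (1 − a + a·h) / (1 − b + b·h).

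*Benefit through prescription* (a = 0.96, b = 0.56):
- h = 0.7: (0.04 + 0.672)/(0.44 + 0.392) = 0.712/0.832 = 0.86
- h = 0.5: (0.04 + 0.48)/(0.44 + 0.28) = 0.52/0.72 = 0.72

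*Benefit through reaching target* (a = 0.95, b = 0.30):
- h = 0.7: (0.05 + 0.665)/(0.70 + 0.21) = 0.715/0.91 = 0.79
- h = 0.5: (0.05 + 0.475)/(0.70 + 0.15) = 0.525/0.85 = 0.62

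**Arm hazard ratio with ULT (any/none) in the model**

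*Benefit through prescription.* At equal prescription status the arms have equal hazards, so the adjusted ratio is 1.00 for either h.

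*Benefit through reaching target.* Among those on ULT, the proportion at target is 0.95/0.96 = 0.990 v 0.30/0.56 = 0.536. With h = 0.7 the relative hazards are 0.703 v 0.839, a ratio of 0.84. Among those not on ULT the ratio is 1.00. A single arm coefficient averages the two strata. With Mantel-Haenszel weights, per unit of person-time in each arm:
- Not on ULT (0.04 v 0.44, total 0.48): 0.04 × 0.44/0.48 = 0.037 in both numerator and denominator.
- On ULT (0.96 v 0.56, total 1.52): numerator 0.96 × 0.703 × 0.56/1.52 = 0.249; denominator 0.56 × 0.839 × 0.96/1.52 = 0.297.
- Adjusted HR = (0.037 + 0.249)/(0.037 + 0.297) = 0.286/0.334 = 0.86.
- Share of log-HR removed: 1 − ln(0.86)/ln(0.79), about one third.

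**Simulation check.** Cox models with yearly ULT status over 4 years, 40,000 participants, 12 runs per scenario, assumed baseline hazard 5% per year:

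| Pathway | h | Arm HR without ULT | Arm HR with ULT | Share of log-HR removed |
|---|---|---|---|---|
| Prescription | 0.7 | 0.86 | 1.00 | 100% |
| Prescription | 0.5 | 0.73 | 1.00 | 99% |
| Reaching target | 0.7 | 0.79 | 0.86 | 34% |
| Reaching target | 0.5 | 0.61 | 0.71 | 31% |

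The standard error of the arm log-HR rises by 14% to 19% in these four scenarios.

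**Confounding.** The simulation was repeated with an unmeasured illness factor that raises the hazard (assumed log-hazard 0.7 per standard deviation) and makes prescription less likely. The arm hazard ratio moved from 0.62–0.84 without the covariate to 1.03–1.41 with it. The mechanism is selection: where nearly everyone is prescribed ULT, the few who are not are the sickest. The opposite assumption about who is prescribed would move the estimate the other way. The documents fix neither direction nor size.

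**The case against.** A reader might infer that the covariate is the intervention itself and that adjusting for it must erase the whole effect. The document does not support that. Section 7.1 describes a nurse-delivered strategy of titration to a urate target, drug switching, education and flare prophylaxis, and usual care may include ULT. The contrast is targeted versus untargeted ULT, so prescription is one mediator. The adjusted value of 1.00 holds only if there is no other pathway, and the protocol's own rationale points elsewhere: sections 3 and 7.3 describe usual-care ULT as mostly low, fixed dosing, and the source trial's arms differ more on reaching target (65 percentage points) than on uptake (40 points). On that pathway about one third of the log-HR is lost. Coding that carried drug and dose would absorb more.

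Three further points are fair. The uptake figures are year-2 values from another trial, and nothing is given for years 3–4. The covariate is confined to secondary extension outcomes: the flare outcomes in 6.1.1 and 6.3.1 and the healthcare-utilisation model do not carry it. Section 8.1 gives the SAP precedence, so an arm comparison without the covariate may be specified there; the SAP is not at hand.

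These points limit the size and reach of the problem. They do not make the stated model estimate the objective in 4.4: under any coding the term is a post-randomisation variable changed by allocation, and 8.5 offers no other survival model.

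**Conclusion.** The point holds. As written, 8.5 conditions on a post-randomisation mediator in the only survival model that it describes. The resulting arm hazard ratio is not the intention-to-treat effect in 4.4, and the model is inconsistent with the RCT approach that 8.5 says it follows.

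That conclusion needs no numerical assumption. Its size does. With the source trial's year-2 figures, any/none coding and an assumed mediator hazard ratio of 0.5 to 0.7, between about one third and all of the arm log-HR is removed. Confounding of unknown direction may be added. The problem concerns death, CKD, myocardial infarction, ischaemic heart disease and stroke in the extension; it does not touch the flare outcomes or the trial's main conclusion.

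**What to change.** In 8.5, state that the main long-term time-to-event comparison is by randomised arm, adjusted for the stratification factors and baseline values only. Move any model with time-varying ULT prescription to a labelled supplementary analysis, state how the covariate is coded, and say that its arm coefficient is not read as the effect of allocation. A method for time-varying confounding, such as a marginal structural model, could be used there but is optional.

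The cost is a change of wording in 8.5, matched in the SAP if needed. It requires no new data and no change to conduct.
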